2.8 Primary and secondary outcome measures

Primary outcome will be evaluated with the auditory hallucination subscale of the *Psychotic Symptoms Rating Scale* (PSYRATS) [68], measured at baseline assessment (T0) and post-treatment assessment (T1). This subscale comprises of 11 items evaluated by interview, which provides a detailed measure of the frequency and the quality of the hallucinations (e.g., negative content, controllability, impact, distress, etc.). The PSYRATS is the instrument that was used to evaluate the primary outcome in the trials of Leff et al. [30], Craig, Rus-Calafell [35] and our research team [4], and the most frequently used scale in CBT trials on AVH. The PSYRATS has excellent psychometric properties (see **Annex V**). Importantly, the PSYRATS measures the multiple concerns expressed by patients during the 3 focus groups performed prior to this grant application. The choice of this primary outcome best captures the multi-component complaints of the 15 schizophrenia patients that were consulted during 3 different focus groups prior to the current grant application. Indeed, during these focus groups, patients expressed concerns not only about the frequency and intensity of the voice, but also about the negative content of the utterances and the distress caused by them.

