2.10 Sample size justification In view of the large effects of AT on AVH observed by available studies [30, 35] and by our pilot data, in addition to the small to moderate effects of CBT [26] on these symptoms, we are expecting to observe a superior efficacy of AT over CBT (f , effect size for the difference on AVH is estimated at 0.25). We thus estimated with G-Power that the recruitment of 52 patients per intervention group will allow to detect superior effects (using pre- and post-therapy assessments) of AT over CBT on auditory hallucinations with a statistical power of 80% and an alpha of 0.05. To include the predicted attrition

of 20% (based on our ongoing trial) and 5 degrees of freedom to control for possible confounders, the total sample to recruit will be 68 per group ($52 \times 2 = 104$; $104 + 5 = 109$; $109 / 0,8 = 136$ total; $136 / 2 = 68$ per group).

2.11 Health service research issues: Our pilot data has been showing a greater improvement in the quality of life of patients after AT compared to CBT. We have thus included the QLS in the trial. The effect size for the difference on quality of life is estimated to be at least moderate (f , effect size of 0.25), which indicates that 68 patients per intervention group is enough to demonstrate the superiority of AT over CBT with a statistical power higher than 80% and an alpha of 0.05.

2.12 Recruitment We did presentations in various centers quarterly, resulting to the referral of at least one patient reference weekly. Since March 2017, we have been able to recruit at least 3 patients per month in the project. The recruitment of 136 schizophrenia patients with treatment resistance within 4 years is feasible (from April 2019 to January 2023) (see **Annex II** for a detailed Timeline).

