2.16 Types of analyses To compare the effects of both interventions (AT and CBTp) on the primary outcome (e.g. AVH) from T0 (baseline) to T1 (end of both therapies), we will perform linear mixed-effects models (LMM) analyses [76-81]. Such analyses have been successfully used by [name] in CIHR-funded RCTs [82, 83]. The major capability of LMM is that it handles unequal variances and correlated data, which are very common in treatment trials. LMM also allows for an unequal number of repetitions. LMM procedure applies both fixed and random effects, which make it suitable for clinical trial data. LMM is based, furthermore, on maximum likelihood methods, versus the usual analysis of variance (ANOVA) methods, which require sphericity of data, and are not robust using small to moderate sample sizes. LMM thus presents a clear advantage over ANOVA methods in modeling real data. There will be a per-protocol analysis and an intention-to-treat analysis with the inclusion of withdrawals to yield a more conservative effect of treatments. Potential differences in socio-demographic variables at baseline will be considered as co-variables. The effects of both interventions on secondary outcomes from T0 to T1, as well as the effects on both interventions on primary and secondary outcomes *during the follow-up* (T2, T3 and T4) will also be assessed using linear mixed models.

2.17 Frequency of analyses A statistician will perform analyses on recruitment rates, retention rates, compliance rates and adverse events every 6 months for the safety data committee. The analysis of primary and secondary outcomes will be performed at the end of the trial.

2.18 Subgroup analyses Due to stratification, an equal number of men and women will be assigned to both treatment arms to examine the gender differences in both interventions. Our primary goal is to show the superior efficacy of AT on AVH. In our pilot data, we did not see any sex nor gender differences in this regard. We will nonetheless ensure this by completing an exploratory analysis on gender at the end of the study.

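### Baseline covariates added as main effects to a T0–T1 mixed model give the primary contrast little or no adjustment; Section 2.16 should state the model form and cross them with visit

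*Combined protocol and SAP*

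**What the plan says.** For the primary outcome, Section 2.16 of the combined protocol and SAP reads "from T0 (baseline) to T1 (end of both therapies), we will perform linear mixed-effects models (LMM) analyses". Its covariate rule is one sentence: "Potential differences in socio-demographic variables at baseline will be considered as co-variables". It does not state the fixed effects, the contrast to be tested, how T0 enters, or whether covariates interact with visit.

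On incomplete data it notes "LMM also allows for an unequal number of repetitions", and on analysis sets "There will be a per-protocol analysis and an intention-to-treat analysis with the inclusion of withdrawals". Secondary outcomes and T2–T4 are also to be analysed with linear mixed models.

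Section 2.10 enlarges the sample by "5 degrees of freedom to control for possible confounders" and expects 20% attrition. On the primary outcome it says "effect size for the difference on AVH is estimated at 0.25" (Cohen's f). Section 2.3 stratifies randomisation by gender and clozapine. Section 2.5 adds that medication changes during follow-up will be controlled for.

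**The concern.** The wording of 2.16 points to a repeated-measures model. It compares the arms over the interval from T0 to T1, relies on the model's tolerance of unequal repetitions, and sets the method against ANOVA with its sphericity requirement. Section 2.8 lists T0 and T1 together as measurements of the primary outcome. Nothing makes T0 a predictor, constrains the baseline means or crosses covariates with time.

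In that model a main-effect covariate shifts a patient's T0 and T1 scores by the same amount and so has little or no bearing on change. The report could then describe the AT–CBTp contrast as adjusted for baseline differences when the adjustment had hardly touched it. The covariate rule is aimed at observed imbalance, which is where adjustment is wanted.

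**Working it through.** **The plan's own figure.** f = 0.25 with two equal groups is d = 2 × 0.25 = 0.5. For the G*Power repeated-measures between-factors test with two measurements, λ = f² × N × 2/(1 + ρ). At N = 104 and ρ = 0.6 this is 0.0625 × 104 × 2/1.6 = 8.125, and power is 0.806. So 104 is reproduced, but only with ρ of about 0.60 to 0.62, which the plan does not state. Then (104 + 5)/0.8 = 136.25, given as 136. The covariate allowance accounts for 5/0.8 = 6.25 recruits.

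**Why the covariate drops out.** Let D = Y(T1) − Y(T0), and let S be the weighted sum of the two scores that is uncorrelated with D. A main-effect covariate x appears in the mean of S but not of D. The arm-by-time contrast is estimated from D alone, so with complete data it is the difference in mean change, with or without x. REML fits confirm this: the contrast and SE are identical under compound symmetry and unstructured covariance, even when x predicts change. If some patients have T0 only, S carries information and x has some influence.

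**Size with complete data.** Assumed: 68 per arm, residual SD 1, T0–T1 correlation 0.6, covariate slope on change 0.3 SD per SD.

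| Model | Residual variance | SE = √(2 × variance/68) | SE from fits |
|---|---|---|---|
| No covariate, or main effect only | 2(1 − 0.6) + 0.3² = 0.89 | 0.162 | 0.162 |
| Covariate × visit | 2(1 − 0.6) = 0.80 | 0.153 | 0.154 |
| T1 given T0 and covariate | 1 − 0.6² = 0.64 | 0.137 | 0.138 |

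Covariate × visit lowers the SE by about 5%. Conditioning on T0 as well lowers it by about 15% (1 − 0.138/0.162). Under a second set of inputs (correlation 0.5, covariates explaining 20% of variance), covariate × visit lowers the SE by 2% when covariates predict change (0.158 to 0.155) and raises it by about 1% when they do not (0.152 to 0.154).

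**Chance imbalance.** The SE of a standardised imbalance is √(2/68) = 0.17, so its mean absolute size is 0.17 × √(2/π) = 0.14 SD. In the fits, the estimate moves 0.31 SD per SD of imbalance both without the covariate and with it as a main effect, against about 0.02 with covariate × visit.
- Typical imbalance: 0.14 × 0.31 = 0.04 SD, and 0.04/0.5 = 8% of d.
- Imbalance of 0.3 SD: 0.3 × 0.31 = 0.09 SD, 18% of d. This is 0.3/0.17 = 1.75 SE, with two-sided probability about 8% per covariate.

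**20% of T1 missing.** If missingness is unrelated to the covariates, adding main effects moves the contrast by a mean of 0.004 to 0.005 SD (first inputs) or 0.013 SD (second inputs, maximum about 0.06). If dropout depends on the covariates differently by arm (second inputs, unstructured covariance, true effect −0.5):

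| Covariate effect | No covariate | Main effect | Covariate × visit |
|---|---|---|---|
| Same at T0 and T1 | −0.602 | −0.529 | −0.528 |
| Also predicts change | −0.655 | −0.579 | −0.504 |

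Each mean has a Monte Carlo error of about 0.17/√150 = 0.014. In the first row the two covariate forms do equally well. In the second, main effects remove about half the bias (0.076 of 0.155) and covariate × visit removes nearly all of it.

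**The case against.** The strongest reply is that the model above is a reading, because 2.16 does not write one out. Its words also fit T0 as a covariate, a constrained baseline or covariate-by-visit terms, and covariates act in all of these. With a constrained baseline, main-effect covariates moved the complete-data contrast by a mean of 0.026 to 0.040 SD. The sample size does not settle the matter. The repeated-measures test that gives 104 is the between-factors one, where a main-effect covariate does adjust; the interaction test gives only 28 to 34 in total at ρ of 0.6 to 0.5. That inference is weak, since ρ is unstated, and a between-arm test averaged over T0 and T1 would include scores taken before randomisation.

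A reader might infer that the covariates cannot change the primary estimate, or that the plan's whole control of confounding does nothing. The documents do not support that. The intention-to-treat analysis keeps withdrawals and 20% attrition is expected, so main-effect covariates can act, and with dropout that depends on them they act usefully. Stratification already balances gender and clozapine. Follow-up medication changes vary over time and do not cancel. The 5 degrees of freedom are not limited to fixed socio-demographic variables.

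These replies limit the strength of the point. They do not show that the plan specifies a model in which the covariates work as intended.

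**Conclusion.** The point holds in conditional form. On the natural reading of 2.16, main-effect covariates leave the primary contrast unadjusted with complete data and nearly so when missingness is unrelated to them; they adjust it partly when dropout depends on them. It would be wrong to conclude that the primary estimate is biased by confounding: under randomisation the unadjusted contrast is unbiased and its SE already allows for chance imbalance. What is lost is some precision, adjustment for the imbalance actually observed, and part of the correction for covariate-dependent dropout.

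The size is modest: about 0.04 SD at a typical imbalance, with 0.09 SD needing an uncommon one, and 2% to 5% of the SE from crossing with visit when covariates predict change. These figures rest on the assumed correlation, slope and dropout patterns, none of which the documents give. The change is worth making because a better model form is available with data already collected.

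**What to change.** In 2.16, write out the fixed effects and the tested contrast. Name a short list of baseline covariates, within the 5 degrees of freedom already budgeted, fixed before unmasking; say whether gender and clozapine are on it. Enter each with its interaction with visit in the likelihood-based mixed model. Preferably also constrain the T0 means to be equal across arms, which is justified because T0 precedes randomisation, or use T0 PSYRATS auditory hallucination score as a covariate, crossed with visit where there are several post-baseline visits. Use the same form for secondary outcomes and T2–T4.

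These are alternative valid forms and not equivalent ones. Conditioning on T0 is more precise than comparing change. A regression of T1 alone drops patients without T1, so the constrained-baseline mixed model fits the stated intention-to-treat analysis better.

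The cost is one or two sentences of SAP wording and degrees of freedom already allowed for, with a slight loss of precision if the chosen covariates turn out not to predict change. No extra patients or data are needed.

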3.1 Day to day trial management

The study coordinator will be responsible of assessing patients' eligibility, obtaining informed consents and enrolling participants in the trial. The coordinator will ascertain intervention assignment by means of an external centralized website for randomization that will be independent of the recruitment process. After the randomization process, the coordinator will contact the corresponding therapist to provide participant information. The coordinator will manage the assessments to evaluators and participants for all time-measures, the inter-rater reliability simulations, and the data handling. He or she will also document medication dosages during follow-up assessments.

The therapists will conduct the 9 weekly sessions and offer support between sessions if needed. Independent counselling psychologists will conduct treatment-integrity evaluations twice yearly based on audio-recorded sessions and grids developed to assess adherence to manualised approaches and skills in delivery.

The independent evaluators having clinical experience with psychotic patients will be masked from objectives, hypotheses and intervention allocations. Inter-rater reliability simulations will be completed every 4 months with the coordinator.

The statistician will be masked from intervention allocations. He will produce outcome analysis at the end of the study and will produce a report to the data safety committee biannually or upon request. Statistical analyses will be performed by [name], a full-time biostatistician at the Mental Health University Institute

of Montreal. He has more than 15 years of experience and he is currently involved with more than 20 researchers at the Centre for different ongoing clinical trials on psychosocial interventions.

Data handling *Data* will be stored and processed anonymously, and codes will be allocated to each patient. We will use coded software designed to store and retrieve research data, which will be converted into SPSS or EXCEL files. Data flow will be monitored on a patient-by-patient basis by the coordinator with a summary file to provide information on patients' current status.

The data safety committee and stopping algorithm The committee will include a researcher with experience on RCT studies, a psychologist or a psychiatrist with clinical experience with this population, a biostatistician knowledgeable about statistical methods for clinical trials and a patient representative. The members will be external to the project. During biannual meetings, the statistician will present the statistics on recruitment rates, retention rates, compliance rates and analysis of adverse and major events, if any (e.g., psychiatric hospitalization). During the therapy, if there is a higher occurrence of a major adverse event in one group compared to the other ($p < 0.1$) the committee will conduct a risk-benefit analysis. If the committee considers the risks to clearly surpass the benefits, the trial will be terminated immediately.

References

1. Goeree, R., et al., *The economic burden of schizophrenia in Canada in 2004*. *Curr Med Res Op*, 2005. **21**(12): p. 2017-2028.
2. Chong, H.Y., et al., *Global economic burden of schizophrenia: a systematic review*. *Neuropsychiatric disease and treatment*, 2016. **12**: p. 357.
3. Meltzer H, K.A., *Treatment-resistant schizophrenia*, in *Comprehensive care of schizophrenia: a textbook of clinical management*, M.R. Lieberman J, Editor. 2001: London: Martin Dunitz. p. 181-203.
4. du Sert, O.P., et al., *Virtual reality therapy for refractory auditory verbal hallucinations in schizophrenia: A pilot clinical trial*. *Schizophrenia Research*, 2018.
5. American Psychiatric Association, *Diagnostic and statistical manual of mental disorders (DSM-5®)*. 2013: American Psychiatric Pub.
6. Schooler, N.R., *Relapse and rehospitalization: comparing oral and depot antipsychotics*. *J Clin Psychiatry*, 2003. **64 Suppl 16**: p. 14-7.
7. Marwaha, S. and S. Johnson, *Schizophrenia and employment - a review*. *Soc Psychiatry Psychiatr Epidemiol*, 2004. **39**(5): p. 337-49.
8. Marwaha, S., et al., *Rates and correlates of employment in people with schizophrenia in the UK, France and Germany*. *Br J Psychiatry*, 2007. **191**: p. 30-7.
9. Kozma, C., et al., *Change in employment status over 52 weeks in patients with schizophrenia: an observational study*. *Curr Med Res Opin*, 2011. **27**(2): p. 327-33.
10. Harvey, P.D., et al., *Functional impairment in people with schizophrenia: focus on employability and eligibility for disability compensation*. *Schizophr Res*, 2012. **140**(1-3): p. 1-8.

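### The only pre-specified between-arm safety trigger covers the therapy weeks alone, so an excess of major adverse events in the 12-month follow-up does not formally prompt a risk-benefit review

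*Combined protocol and SAP*

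**What the plan says.** The trigger is in Section 3.1, under the data safety committee and stopping algorithm. It begins "During the therapy, if there is a higher occurrence of a major adverse event in one group compared to the other", with p < 0.1 as the threshold. If it is met, "the committee will conduct a risk-benefit analysis", and then: "If the committee considers the risks to clearly surpass the benefits, the trial will be terminated immediately". Psychiatric hospitalization is the example given of a major event. No test, sidedness or event rate is stated, and no comparative trigger is given for the period from T1 to T4.

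Therapy is nine weekly sessions (2.6). T1 falls in the week after the last session (2.1), and follow-up visits come 3, 6 and 12 months after T1 (2.7). Recruitment of 136 patients, 68 per arm, is planned from April 2019 to January 2023 (2.10, 2.12).

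On what the committee sees, Section 2.17 says "A statistician will perform analyses on recruitment rates, retention rates, compliance rates and adverse events every 6 months for the safety data committee", and then "The analysis of primary and secondary outcomes will be performed at the end of the trial". Section 3.1 says of the statistician: "The statistician will be masked from intervention allocations", and "He will produce outcome analysis at the end of the study and will produce a report to the data safety committee biannually or upon request".

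**The concern.** A stopping rule mainly protects people not yet treated. Here early participants complete a year of follow-up while others are still being randomized, so their follow-up events are exactly the information that could protect later patients. The rule's own example of a major event is not confined to the therapy weeks. If one intervention led to more hospitalizations after session 9, the pre-specified comparison would not count them. Any review would then depend on the committee choosing to act outside the written rule.

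There is also a smaller point. The committee is asked to weigh risks against benefits, but no outcome summary is planned before the end of the trial. The text does not say what the benefit side of that judgement would rest on.

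**Working it through.** The stopping rule states no operating characteristics, so there is no figure of the plan's own to reproduce. The 68 per arm is taken as given.

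**1. Share of scheduled time inside the window.** Therapy is 9 weeks and follow-up is 52 weeks after T1. Counting only these, 9/(9 + 52) = 9/61 = 14.8%. Adding up to one week between T0 and the first session and one week to T1, 9/(1 + 9 + 1 + 52) = 9/63 = 14.3%. About 85% of scheduled time lies outside the trigger. This is a share of time, not of events.

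**2. Overlap with enrolment.** April 2019 to January 2023 is 45 months. A participant reaches T4 about 10 + 52 = 62 weeks after starting, and 62/52 × 12 = 14.3 months. The first participants therefore finish follow-up with about 45 − 14 = 31 months of enrolment left.

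**3. An excess confined to follow-up.** Assume equal therapy-window risk of 4% in each arm, 68 per arm, one look and a two-sided Fisher test at p < 0.1. Summing the binomial probabilities over all crossing tables gives a 2.7% chance of crossing, of which 1.3% is in the direction of the arm that later does worse. That figure does not change with the size of the follow-up excess.

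**4. A constant excess.** Assume a constant hazard, so that the risk by week t is 1 − (1 − annual risk)^(t/52). For annual risks of 10% and 20%, the risks are 0.020 and 0.042 at 10 weeks (through T1), and 0.118 and 0.234 at 62 weeks (through T4). Exact probability of crossing, same test, one final look, 68 per arm:

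| Assumed annual risks | Events through T1 (10 weeks) | Events through T4 (62 weeks) |
|---|---|---|
| 10% vs 20% | 5% | 46% |
| 10% vs 30% | 20% | 92% |
| 20% vs 30% | 8% | 36% |
| 20% vs 40% | 22% | 83% |
| 30% vs 50% | 23% | 77% |

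The documents support none of these rates. The table shows only how much the window leaves out over a range of assumptions.

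**5. Cost of the wider window.** Six-monthly looks over 45 months give about 45/6 = 7.5, so seven looks were simulated with equal risks in both arms and a two-sided Fisher test. The chance of at least one crossing is about 4% at a 4% event risk and about 16% at a 20% event risk. The second figure moves by about a percentage point with the spacing of the looks. Looks after enrolment closes would add somewhat to both.

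**6. Outcome information.** Section 3.1 requires a risk-benefit analysis once the trigger is met. Section 2.17 lists the periodic content as recruitment, retention, compliance and adverse events, and places outcome analysis at the end. Section 3.1 separates the outcome analysis from the committee report, allows that report on request, and does not define what a requested report contains.

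**The case against.** The best defence is that follow-up events are not hidden. The six-monthly adverse-event analyses carry no time limit, assessments are identical at every time point (2.9), and nothing bars an external committee that includes a biostatistician from acting on what it sees. This stands. A reader might infer that a follow-up excess would never reach the committee or could never lead to a review, and the documents do not support that. What is limited is the formal trigger.

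The window also has a rationale. The research team offers no treatment after T1 (2.1), and the main risk named in 1.5 is tolerability of the first avatar sessions, which falls inside it. That explains why the therapy weeks are covered but gives no reason to leave out later events while enrolment is open. The opening words might also be read loosely as the time when the trial is delivering therapy to anyone. If that was meant, a clause should say so.

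A reader might further infer that the committee would have no benefit data and could not carry out its review. That goes too far. Baseline and T1 PSYRATS scores will exist, a report can be requested without a stated limit on content, and deferring planned efficacy analysis to the end is ordinary practice. The gap is only that no outcome summary is planned or described for this purpose.

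Finally, it is tempting to call the trigger insensitive because 4 versus 0 events would not cross it. That depends on a test the protocol does not name. At 68 per arm, 4 versus 0 gives p = 0.119 by two-sided Fisher, 0.060 by one-sided Fisher and 0.042 by uncorrected chi-square. No claim is made here on that ground.

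**Conclusion.** The point holds as a gap in the formal rule. The only pre-specified between-arm safety comparison covers about 15% of each participant's scheduled time, and an excess of major adverse events after session 9 does not formally prompt the risk-benefit review while later patients are still being randomized. Informal review through the six-monthly reports softens this but does not replace a written trigger. The conclusion rests on the plain reading of the opening words of the rule and on the visit schedule. It does not depend on the crossing probabilities, which assume a two-sided Fisher test, constant hazards, a single final look and event rates that the documents do not give. The question of outcome information for a triggered review is secondary and is one of wording to reconcile.

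**What to change.** In Section 3.1, apply the same between-arm comparison to all major adverse events from randomization through T4, by randomized arm under coded labels. Name the test and its sidedness, and say who prepares the comparison, since the statistician is masked and the documents do not say who would supply coded groups. If the therapy-only window is intended, state that and give the reason.

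Separately, reconcile Sections 2.17 and 3.1 on what outcome information, if any, the committee receives when a review is triggered. Whether that should include a closed by-arm outcome table is open to debate, and the main change does not depend on it.

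The cost is protocol or charter wording, since adverse events are already analysed every six months. The downside is more reviews prompted by chance over repeated looks, at the illustrative 4% to 16% shown above. Each crossing prompts a review and does not by itself stop the trial.
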